5.4.3 Safety Follow-up Phase

Patients will complete participation in the protocol at the time of surgery and will not be followed unless the patient requires follow up of adverse events. The following evaluations and procedures will be performed at **early termination**. Every effort should be undertaken for the following procedures to be completed within 10 days.

- Clinical evaluations: Weight, physical examination (complete), vital signs and performance status. There must be a complete and clear documentation of objective response or disease progression using the RECIST criteria. Reason(s) for discontinuation must be documented.
- Laboratory assessment: UA, CBC with differential and platelet count, serum chemistries (glucose, BUN, creatinine, total protein, albumin, bilirubin, calcium, alkaline phosphatase, AST, and ALT), serum electrolytes (Na, K, Cl), and lipid panel (cholesterol, triglycerides, HDL, and LDL) in a fasting state (at least 8 hours).
- Tumor assessments: Mammogram, breast ultrasound, and breast MRI. Spiral CT scans of chest, abdomen, and pelvis, bone scan, and any other procedure are not required per protocol but will be obtained if clinically indicated.
- Concomitant medication assessment.
- Assessment of adverse events. If the patient has an ongoing toxicity, the patient should be followed until resolution or stabilization. Serious and non-serious adverse events occurring

within 30 days of day 0 of the last treatment should be reported on the appropriate adverse event CRF.

5.5 Study Termination

The principal investigator retains the right to terminate study participation in consultation with the other investigators in the study. The principal investigator will notify the institutional review board and FDA in writing of the early termination or completion of the study and keep a copy of the notification in the regulatory file. Circumstances that may raise consideration for early termination include but are not limited to: inordinate toxicity of the proposed combination that is not amenable to protocol amendment, and slow accrual (rate of accrual of less than 1 patient in 6 months).

5.6 Subject Discontinuation

Patients may withdraw from this study at any time. Any patient who withdraws will be encouraged to return to the study center for the post-dose evaluations. The termination visit consists of all evaluations scheduled for the termination visit. The primary reason(s) for discontinuation must be recorded on the appropriate CRF page.

The PI may discontinue a patient from treatment. Reasons may include, but are not limited to, the following: progressive disease, failure to obtain postmenopausal status (defined as serum estradiol levels any time during treatment in the premenopausal range) clinically significant deterioration, noncompliance, persistent grade 3 or 4 adverse event or any significant adverse event that compromises the patient's ability to participate in the study, requirement of a significant surgical procedure or radiation therapy during the treatment period of the study, investigator's determination that it is not in the patient's best interest to continue participation, anemia greater than grade 4, persistent grade 3 mucositis despite maximal supportive care, development of brain metastases, pregnancy.

Patients who have an ongoing grade 4 or serious adverse event at the time of discontinuation from study treatment will continue to be followed at least weekly for 4 weeks and at least monthly thereafter at the discretion of the investigator until resolution of the event or until the event is considered irreversible.

6. STUDY DRUG PREPARATION AND DISPENSATION

6.1 Dosing Regimen and Schedule

Table 6-1: Dosing regimen and schedule

Drug	Formulation	Dose and Route	Frequency
Letrozole	Tablet for oral use	2.5 mg PO	Daily
Everolimus	Tablet for oral use	5 or 10 mg PO	Daily
TRC105	Solution for intravenous infusion	10 or 15 mg/kg IV	q 2 weeks*
Goserelin**	Depot for subcutaneous injection	3.6 mg subcutaneously	q 4 weeks

* The first infusion of TRC105 will be split in 2 separate infusions to be administered on cycle 1 day 1 (3 mg/kg) and cycle 1 day 4 (12 or 7 mg/kg).

** when applicable

6.1.2 TRC105 Preparation

TRC105 will be prepared in the pharmacy and diluted into normal saline using appropriate aseptic technique. TRC105 will be administered using an in-line 0.2 micron filter. No incompatibilities between TRC105 and polyvinyl chloride or polyolefin bags have been observed. Multiple vials will be required for a single dose. The following formulae should be used to calculate the volume of TRC105 to be added to normal saline:

- Patient weight (kg) × dose level (mg/kg) divided by TRC105 concentration (mg/mL) = volume of TRC105 (mL) to be administered.

The volume of TRC105 that is to be administered can be rounded up or down to the nearest 1.0 mL; in the case of an increment of 0.5 mL the volume should be rounded up. **The maximum weight that should be used for dose calculation in this study is 85 kg (note: there is not a weight restriction for enrollment purposes).** If the patient’s weight changes by > 10% during the study, the dose of TRC105 will be recalculated. At that time a new baseline weight will be established such that subsequent weight changes by >10% from the new baseline weight would require further recalculation of the TRC105 dose. The calculated volume of TRC105 will be diluted with normal saline. Appropriate judgment should be exercised in withdrawing an adequate amount of saline necessary to permit injection of the appropriate volume of antibody into a normal saline bag in accordance with the dose needed. The final TRC105 concentration must be between 0.3 mg/mL and 10 mg/mL. The prepared TRC105 must be gently inverted several times in order to ensure a homogeneous solution. The diluted infusion solution of TRC105 should be used within 8 hours of preparation if stored at room temperature, or within 24 hours of dilution if stored at 2°C to 8°C (36° to 46°F). The expiration time should be labeled on the bag. If the diluted infusion solution of TRC105 cannot be infused within 8 hours of preparation (i.e.: the prepared infusion is at room temperature for more than 8 hours), a second bag will be prepared that contains the balance of the planned dose that was not already delivered. The prepared solution should not be frozen.

6.1.3 TRC105 Administration

Patients should be encouraged to drink abundant fluid (e.g. two eight ounce glasses of water or juice) prior to the first treatment. Intravenous hydration prior to and during therapy is left to the discretion of the Investigator, but should be considered if the patient is thought to be volume depleted.

The following TRC105 premedications should be administered 2 hours to 30 minutes prior to the start of each infusion:

- Acetaminophen 650 mg p.o. x 1
- Methylprednisolone 100 mg i.v. In the absence of any infusion reaction with the prior dose, methylprednisolone may be discontinued beginning with **cycle 3**. In addition, methylprednisolone will be given in the case of a delay of ≥ 18 days between any two doses or if the patient develops an infusion reaction during the immediate prior infusion.
- Famotidine 20 mg i.v. or p.o. (or similar H2 blocker) x 1. Famotidine (or similar H2 blocker) may be discontinued starting with Cycle 2 in the absence of infusion reactions with the prior dose.
- Cetirizine 10 mg i.v. or p.o. x 1 (or similar oral or intravenous antihistamine). Cetirizine (or similar oral or intravenous antihistamine) may be discontinued starting with Cycle 2 in the absence of infusion reactions with the prior dose.

TRC105 will be administered intravenously utilizing an infusion pump. TRC105 has been demonstrated to be compatible with polyethylene lined, non-DEHP infusion sets and polyvinyl chloride, non-DEHP infusion sets. TRC105 is required to be administered with a 0.2 micron downstream filter. The attachment of the infusion pump administration set to the i.v. bag and transport of the TRC105 study drug to the patient will be performed as per standard study site procedures.

Following the appropriate premedication regimen, the patient will receive TRC105 on day 1 and day 15 of every cycle. The first TRC105 dose will be split with 3 mg/kg administered on cycle 1 day 1 and infused over 4 hours (+/- 15 minutes) and 12 mg/kg (or 7 mg/kg if dose is de-escalated) administered on cycle 1 day 4 and infused over 2 hours (+/- 15 minutes), and then the full dose of 15 mg/kg (or 10 mg/kg if dose is de-escalated) given on cycle 1 day 15 and every 2 weeks thereafter and will be administered over a minimum of 90 minutes. The patient must complete at least one 4 hour infusion (+/- 15 minutes) without the development of any infusion reactions, in order to reduce the subsequent TRC105 infusion to 2 hours (+/- 15 minutes) and complete a 2 hour infusion (+/- 15 minutes) without the development of any infusion reactions in order to reduce subsequent TRC105 infusions to a **minimum of 90 minutes**. If the patient develops infusion reactions of any kind they should be managed appropriately (see [Section 5.3.2.1](#)) and the patient is not permitted to reduce the duration of the next planned infusion.

The rate of TRC105 infusion must not exceed 25 mg/min. When the i.v. bag containing TRC105 is empty, flush the i.v. line with a 20 mL normal saline. The dose level, time of transfer to i.v. bag, and the infusion start and stop times must be recorded in the source documents.

If the patient misses a TRC105 dose (i.e., ≥ 18 days between doses), the full premedication (including methylprednisolone) should be reinstated as per the initial infusion and TRC105 dose should be administered over two days as was done for the initial dose.

6.2 Drug Formulations

All dosages prescribed and dispensed to the patient and all dose changes during the study must be recorded. Medication labels will comply with US legal requirements and be printed in English. They will supply no information about the patient.

6.2.1 Letrozole Formulation

Commercially available tablets of letrozole will be used in the study. Complete guidelines for the management and administration of letrozole can be found in the package insert (http://www.accessdata.fda.gov/drugsatfda_docs/label/2014/020726s027lbl.pdf). Letrozole will not be provided from the study

6.2.2 Everolimus Formulation

Everolimus is formulated as tablets for oral administration of 2.5mg, 5mg, and 10mg strength. Tablets are blister-packed under aluminum foil, which should be opened only at the time of administration as drug is both hygroscopic and light-sensitive. Everolimus should be administered orally once daily at the same time every day, either consistently with or consistently without food. Refer to label for expiration date and storage conditions.

The extent of absorption of everolimus through topical exposure is not known. Therefore, caregivers are advised to avoid contact with suspensions of everolimus Tablets. Hands should be washed thoroughly before and after preparation of either suspension. The blisters for everolimus tablets should be opened only at the time of administration as the formulation is both hygroscopic and light-sensitive. Storage conditions for everolimus are described on the medication label (http://www.accessdata.fda.gov/drugsatfda_docs/label/2014/022334s021s023s024,203985s002s004s005lbl.pdf). The study drugs should be stored in a secure, locked area while under the responsibility of the principal investigator. Receipt and dispensing of study drug must be recorded by an authorized person at the investigator's site.

The tablets should be swallowed whole with a glass of water and should not be chewed or crushed. For patients unable to swallow tablets, the tablet(s) should be dispersed completely in a glass of water (containing approximately 30 mL) by gently stirring until the tablet(s) is fully disintegrated (approximately 7 minutes), immediately prior to drinking. The glass should be rinsed with the same volume of water and the rinse completely swallowed to ensure the entire dose is administered. If vomiting occurs, no attempt should be made to replace the vomited dose. Patients should be instructed that if they miss a dose on one day, they must not take any extra dose the next day, but instead to immediately contact the study center as soon as possible to ask for advice. Everolimus will be provided from the study.

6.2.3 TRC105 Formulation

TRC105 is a sterile, clear colorless to slightly yellow opalescent solution for intravenous (IV) infusion. The solution may contain small amounts of visible particulates. TRC105 will be filtered through a 0.2 µm low protein binding filter at the clinical site prior to administration. TRC105 will be supplied in 100 and 400 mg single-use vials in 20 mM L-Histidine/L-Histidine Monohydrochloride, 240 mM Trehalose, 0.01% Polysorbate 20 (25 mg TRC105/mL). Vials will be labeled with the following:

TRC105 NSC# 754227 100 mg per vial (25 mg/mL, 4 mL per vial) Store refrigerated at 2-8°C. For Intravenous Use Only. Single-use vial. Lot: XXXXXXXX Mfg Date: XX/XX/XXXX Caution: New Drug Limited by Federal (or United States) law to investigational use. TRACON Pharmaceuticals Inc., San Diego, CA 92122 USA
	
TRC105 NSC# 754227 400 mg per vial (25 mg/mL, 16 mL per vial) Store refrigerated at 2-8°C. For Intravenous Use Only. Single-use vial. Lot: XXXXXXXX Mfg Date: XX/XX/XXXX Caution: New Drug Limited by Federal (or United States) law to investigational use. TRACON Pharmaceuticals Inc., San Diego, CA 92122 US

---	---

TRC105 will be provided by TRACON Pharmaceuticals, Inc.

6.2.4 Goserelin Formulation

Goserelin is supplied as a sterile, biodegradable product containing goserelin acetate equivalent to 3.6 mg of goserelin. Goserelin is designed for subcutaneous injection with continuous release over a 28-day period. Goserelin acetate is dispersed in a matrix of D,L-lactic and glycolic acids copolymer (13.3-14.3 mg/dose) containing less than 2.5% acetic acid and up to 12% goserelin-related substances and presented as a sterile, white to cream colored 1-mm diameter cylinder, preloaded in a special single use syringe with a 16-gauge x 36 +/- 0.5 mm siliconized needle with protective needle sleeve (SafeSystem™ Syringe) in a sealed, light and moisture proof, aluminum foil laminate pouch containing a desiccant capsule. Studies of the D,L-lactic and glycolic acids copolymer have indicated that it is completely biodegradable and has no demonstrable antigenic potential (AstraZeneca, Package Insert).

6.3 Study Drug Storage and Handling

Study treatments must be received by designated personnel at the study site, handled and stored safely and properly, and kept in a secured location to which only the investigator and designated site personnel have access. Upon receipt, the study treatment should be stored according to the instructions outlined in section 6.2.

6.4 Study Drug Compliance

The investigator should promote compliance by instructing the patient to take the study drug exactly as prescribed and by stating that compliance is necessary for the patient’s safety and the validity of

the study. The patient should be instructed to contact the investigator if he/she is unable for any reason to take the study drug as prescribed.

Compliance will be assessed by the investigator and/or study personnel at each patient visit and information provided by the patient and/or caregiver. Records of study medication used, dosages administered, and intervals between visits and the completion of the study will be captured in the Drug Accountability Form. This information must be captured in the source document at each patient visit.

On PK sampling days, compliance will be assured by administration of the study treatment under the supervision of investigator or his/her designee, and will be verified by determination of letrozole, everolimus, and TRC105 in serum.

6.5 Study Drug Accountability

The investigator or designee must maintain an accurate record of the shipment and dispensing of study treatment in a drug accountability log. Patients will be asked to return all unused study treatment and packaging at the end of the study or at the time of study treatment discontinuation.

At study termination, and, as appropriate during the course of the study, the investigator will return all used and unused study treatment, packaging, drug labels, and a copy of the completed drug accountability log to the Novartis and TRACON monitor or to the Novartis and TRACON address provided in the investigator folder at each site.

[figure not shown]
7. VISIT SCHEDULE AND ASSESSMENTS

7.1 Study Flow and Visit Schedule

Figure F and **table 7-1** (following page) list all the assessments and indicate with an “x” the times they need to be performed.

Baseline evaluations are to be conducted within 1 week prior to start of protocol therapy. Imaging studies must be done within 4 weeks prior to the start of therapy. In the event that the patient's condition is deteriorating, laboratory evaluations should be repeated within 48 hours prior to initiation of the next cycle of therapy. For all visits except day 1, there is a temporal window of ± 3 days to account for holidays, inclement weather or other extraneous circumstances. The temporal window does not apply for PK sampling, which needs to be undertaken at the specified time frames. Every effort must be undertaken to follow this schedule.

In patients who discontinue their treatment early, all procedures outlined in 5.4.3 (5.4.3 **Safety Follow-up Phase**) must occur within 10 days. Patients who complete the protocol treatment and proceed to surgery as planned do not need to have an end of treatment visit.

Premenopausal women at the time of study enrollment will receive goserelin 3.6 mg subcutaneously q 4 weeks to achieve ovarian suppression.

7.2 Measurement of Effect

Although response is not the primary endpoint of this trial, patients with measurable disease will be assessed by standard criteria. **Patients must have disease that can be measured and followed by mammogram and/or breast ultrasound. Dedicated breast MRI evaluation will be done baseline, week 12 and 24.** For the purposes of this study, patients should be re-evaluated every 4 weeks.

7.2.1 Antitumor Effect

Response and progression will be evaluated in this study using the new international criteria proposed by the Response Evaluation Criteria in Solid Tumors (RECIST)¹¹⁸ Committee (http://ctep.cancer.gov/protocolDevelopment/docs/recist_guideline.pdf)¹¹⁸. Changes in only the largest diameter (one-dimensional measurement) of the tumor lesions are used in the RECIST criteria.

Table 7-1: Study Calendar (see 5.4 Study Procedures)

	SC	Treatment Phase ^{11, 13}												End of treatment ⁷	Follow up	
		C1D1	C1D4	C1D15	C2D1	C2D15	C3D1	C3D15	C4D1	C4D15	C5D1	C5D15	C6D1			C6D15
Informed consent	X															
Demographics	X															
Inclusion/Exclusion	X															
Past Medical History	X															
History Present Illness	X															
Concurrent Medications		X-----X														
Prior therapy	X															
Physician Visits	X	X			X		X		X		X		X		X	X
Physical Examination	X	X			X		X		X		X		X		X	X
Performance status	X	X			X		X		X		X		X		X	X
Vital Signs	X	X			X		X		X		X		X		X	X
Height/Weight	X	X			X		X		X		X		X		X	X
CBC and differential	X		X		X		X		X		X		X		X	X
Chemistries/Electrolytes	X		X		X		X		X		X		X		X	X
FSH, LH,estradiol levels	X															
Estradiol levels ¹⁵					X				X				X			
Pregnancy test ¹⁴	X															
Lipid panel ¹	X				X											
Hepatitis panel ²	X															
Urinalysis ³	X															
12-lead EKG	X															
Serum ferritin level	X															
Everolimus serum level		X ¹⁰			X ¹⁰											
TRC105 serum level		X ¹⁰			X ¹⁰											
Anti-TRC105 antibodies (APA) ¹¹		X			X		X		X		X		X			X ¹¹
VEGF-A serum ¹²	X			X	X											X
sEng / TGF-β serum ¹²	X			X	X											X
Angiopoietin-1/2 serum ¹²	X			X	X											X
Research Biopsy ⁴	X				X											X
Adverse Events		X-----X														

Mammography	X														X	
Breast ultrasound	X				X		X		X		X		X		X	
Breast MRI ⁵	X								X						X	
Body CT/MRI/PET ⁶	(X)															
Letrozole ⁸	X-----X															
Everolimus ⁹	X-----X															
TRC105 ⁹		X	X	X	X	X	X	X	X	X	X	X	X	X	X	
Goserelin ¹³		X			X		X		X		X		X			
Surgery															X	

Notes:

1. Cholesterol, triglycerides, HDL, and LDL in a fasting state (8 hours) should be obtained at least on cycle 2 and, if elevated, repeat on each cycle until recovery to baseline value or grade 1.
2. Hepatitis panel should be obtained on screening and repeated as clinically indicated (HBV-DNA, HBsAg, HBs Ab, and HBc Ab, and RNA-PCR).
3. Urinalysis should be obtained on screening and repeated as clinically indicated.
4. Research biopsy (core needle biopsy of the tumor).
5. Breast MRI is required by the protocol.
6. As clinically indicated after baseline diagnosis.
7. Within a week of surgery.
8. Continuation until the day prior to surgery.
9. Continuation no later than 4 weeks prior to surgery.
10. Samples will be collected and concentrations of the agents measured on cycles 1 and 2 at the following time points: pre-dose, 1, 2, 4, 6, and 24, hours, and cycle 1 day 4 pre-dose.
11. TRC105 anti-product antibodies (APA) will be collected before dosing on cycle 1 day 1, every 4 weeks thereafter, 4 and 12 weeks following the last dose of TRC105.
12. Markers of angiogenesis (VEGF-A, soluble VEGFR2, activin A and activin B, angiopoietin-1 and -2, TGF- β , soluble endoglin) will be measured on samples collected pre-dose, cycle 1 day 15, cycle 2 day 1, and prior to surgery.
13. Administered only if FSH, LH, and estradiol NOT within postmenopausal range at the time of enrollment.
14. In women with childbearing potential
15. Only in women receiving goserelin

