Letrozole 2.5 mg PO daily, continuously until the day prior to surgery. TRC105 15 or 10 mg/kg IV every two weeks until 4 weeks prior to surgery. The first dose of TRC105 will be split into two doses; see Table 7-1 ([Study Calendar](#)) for additional details. Everolimus 5 or 10 mg PO daily, continuously until 4 weeks prior to surgery. Premenopausal women at the time of study enrollment will receive goserelin 3.6 mg subcutaneously q 4 weeks to achieve ovarian suppression.

Main Criteria for Inclusion/Exclusion:

Key Inclusion Criteria

- Recent diagnosis of hormone receptor positive and HER2 negative breast cancer.
- Stage 2 and 3 hormone receptor positive and HER2 negative breast cancer (stage T2-4 but not inflammatory, N0-2, M0).

- Histological grade I, II or III according to the modified Bloom Richardson scale⁵².
- No prior treatment specific for breast cancer.
- Menopausal status as defined by the National Comprehensive Cancer Network. Premenopausal women are eligible if ovarian suppression is achieved with goserelin
- ECOG performance status ≤ 2 (Karnofsky $\geq 60\%$).
- Must have signed study-specific informed consent.
- Liver Function Tests ≤ 2.5 times the upper normal limit (UNL).
- Staging workup: medical/surgical/radiation therapy evaluation, CT scans and bone scan.
- Lipid profile (cholesterol and triglycerides).
- ANC $\geq 1,500/\text{mm}^3$, platelets $\geq 100,000/\text{mm}^3$, Hemoglobin $\geq 10\text{g}\%$.
- Renal function: serum creatinine ≤ 1.5 institutional UNL or creatinine clearance $> 40 \text{ cc/min}$.

Key Exclusion Criteria

- Inflammatory breast cancer.
- Pregnancy.
- Metastatic disease.
- HER2 positive breast cancer by immunohistochemistry or FISH.
- Triple negative breast cancer (hormone receptor and Her2 negative).
- Disease that cannot be followed by imaging studies.

Safety Assessments:

- Vitals signs
- Weight
- ECOG performance status
- Hematology
- Chemistry
- Lipid profile
- Hepatitis panel
- Adverse events
- Concomitant medications

Efficacy Assessments:

- Physical examination
- Imaging studies (mammography, breast ultrasound, breast magnetic resonance imaging)
- Surgical Pathology

Other Assessments:

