3.2.5 Determined menopausal status. Postmenopausal status is defined according to the National Comprehensive Cancer Network¹⁰³

- a. age >60 years old **OR**
- b. prior bilateral oophorectomy regardless of age
- c. if patient <60 years old and amenorrheic for >12 months in the absence of ovarian suppression, FSH and estradiol have to be in the postmenopausal range

women who do not meet these criteria will be determined as non-postmenopausal and will require goserelin subcutaneously q 4 weeks to achieve ovarian suppression.

3.2.6 No prior treatment with therapeutic intent for breast cancer.

3.2.7 No life threatening parenchymal disease or rapidly progressing disease warranting cytotoxic chemotherapy.

3.2.8 Patients must have disease that can be measured and followed by mammogram and/or breast ultrasound (in special cases a dedicated breast MRI may be clinically indicated). The target lesion must not have been previously irradiated.

3.2.9 Resectable/Operable or potentially resectable/operable breast cancer as determined by the treating surgical oncologist.

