5.4 Study Procedures

5.4.1 Screening phase

Informed consent will be obtained before study-specific screening evaluations are performed. Screening evaluations must be performed within 4 weeks prior to day 0. Results of tests or examinations done as standard of care prior to obtaining informed consent and within 56 days prior to day 0 may be used rather than repeating tests.

The following evaluations and procedures will be performed during the screening phase:

- Signed informed consent.
- Clinical evaluations: medical history, demographics, weight and height, complete physical examination, vital signs and performance status.
- Determination of the surgical procedure to be performed at the time of diagnosis without the neoadjuvant treatment by the surgical oncologist in the multidisciplinary team. Determinations include unresectable (for locally advanced disease that cannot be adequately resected unless tumor shrinkage is achieved), mastectomy, and lumpectomy.
- Laboratory assessment: UA, CBC with differential and platelet count, serum chemistries (glucose, BUN, creatinine, total protein, albumin, bilirubin, calcium, alkaline phosphatase, AST, and ALT), serum electrolytes (Na, K, Cl), ferritin, and a lipid panel (cholesterol, triglycerides, HDL, and LDL) in a fasting state (at least 8 hours).
- Determination of menopausal status: FSH, LH, and estradiol levels.
- Pregnancy test in women with childbearing potential.
- Research biopsy (core needle biopsy of the tumor) (required).
- Sentinel lymph node biopsy if required.

- Estrogen and Progesterone receptor status.
- Her-2-neu by immunohistochemistry and or FISH (Negative: IHC 0, 1 or 2+ or non-amplified by FISH).
- Tumor assessments: Mammogram and breast ultrasound are required. PET/CT scan or CT scan of chest, abdomen, pelvis, with bone scan will be obtained. If the scan shows disease outside the breast and/or the axilla, the patient will not be enrolled in the trial.
- 12-lead EKG. Evaluation of the ejection fraction with an echocardiogram or MUGA, if clinically indicated.
- Concomitant medication assessment.
- Patients who have satisfied basic eligibility criteria will be assigned with a study patient number and the patient can proceed to be consented.
- Hepatitis B and C panels (see 5.2.2.3, table 5-2 and table 5-4 for Hepatitis B and C interpretation).

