5.4.2 Treatment Phase

The following evaluations and procedures will be performed during the **treatment phase**: (All assessments should be performed within 5 working days of the protocol-specified date).

- Physical examination, vital signs, weight, and performance status on weeks 4, 8, 12, 16, 20 and 24.
- Laboratory assessments: CBC with differential and platelet count, serum chemistries (glucose, BUN, creatinine, total protein, albumin, bilirubin, calcium, alkaline phosphatase, AST, and ALT), and serum electrolytes (Na, K, Cl) on week 1 and at the beginning of each cycle until week 24.
- Lipid panel (cholesterol, triglycerides, HDL, and LDL) in a fasting state (at least 8 hours) should be obtained at least on cycle 2 and, if elevated, repeated on each cycle until recovery to baseline value or grade 1 (see 5.2.2.2 for management of hyperlipidemia and hyperglycemia).

Serum estradiol levels on weeks 4, 12, and 20 in women receiving goserelin.

- Hepatitis panel as clinically indicated.
- Research biopsy (core needle biopsy of the tumor) at week 4 (required).
- Tumor assessments: Ultrasound of the breast will be obtained on week 4, 8, 12, 16, 20 and 24. Mammogram will be obtained on week 24. Additional PET scans or CT of the chest, abdomen, and pelvis, or bone scans are not required during treatment phase except as clinically indicated (see section **7.2 Measurement of Effect**). MRI breast will be obtained at baseline, week 12 and 24.
- Evaluation of the ejection fraction with an echocardiogram/MUGA only as clinically indicated.
- Surgical evaluation at the end of neoadjuvant therapy. **There must be at least 4 weeks between the last dose of everolimus and TRC105 and surgery.** Patients will continue letrozole until the day before surgery.
- Concomitant medication assessment.
- Assessment of adverse events.

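### Table 7-1 note 13 withholds goserelin from some women for whom section 3.2.5 requires it, and those women then have no scheduled estradiol test during treatment

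*Combined protocol and SAP*

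**What the plan says.** Section 3.2.5 gives three routes to postmenopausal status. Criterion (a) is "age >60 years old" and (b) is prior bilateral oophorectomy. Criterion (c) covers the "patient <60 years old and amenorrheic for >12 months in the absence of ovarian suppression, FSH and estradiol have to be in the postmenopausal range". A default clause deals with everyone else: "women who do not meet these criteria will be determined as non-postmenopausal and will require goserelin subcutaneously". The synopsis uses the same framework: "Menopausal status as defined by the National Comprehensive Cancer Network. Premenopausal women are eligible if ovarian suppression is achieved with goserelin". Section 7.1, which introduces the calendar, repeats that women premenopausal at enrollment receive goserelin, without defining the term.

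The goserelin row of Table 7-1 carries note 13: "Administered only if FSH, LH, and estradiol NOT within postmenopausal range at the time of enrollment". It has no age, oophorectomy or amenorrhea condition.

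Section 5.4.1 lists a screening item: "Determination of menopausal status: FSH, LH, and estradiol levels". During treatment, section 5.4.2 schedules "Serum estradiol levels on weeks 4, 12, and 20 in women receiving goserelin", and note 15 to Table 7-1 sets the same limit: "Only in women receiving goserelin".

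**The concern.** Both 3.2.5 and note 13 tell staff who gets goserelin, and they use different tests. Section 3.2.5 does not accept in-range hormones alone as proof of menopause in a woman under 60 with ovaries; it also asks for more than 12 months of amenorrhea. Note 13 looks only at the hormones, and its wording is restrictive: outside the stated condition, goserelin is not given.

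What is at stake is treatment of an individual woman. Section 2.1.10 says aromatase inhibitors are contraindicated before menopause, and section 4.4 says premenopausal women cannot receive them unless made postmenopausal. A woman whom 3.2.5 classes as non-postmenopausal could be given letrozole without suppression. The monitoring would lapse with it, because on-treatment estradiol depends on receiving goserelin. Section 5.6 lets the investigator discontinue a patient whose estradiol is in the premenopausal range at any time during treatment, but for her no scheduled test would supply that value.

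**Working it through.** The plan gives no figure to reproduce, so the check applies both rules to the same women.

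**Rules.** Under 3.2.5, goserelin is required if (a), (b) and (c) all fail. Criterion (a) needs age above 60. Criterion (b) needs bilateral oophorectomy. Criterion (c) needs age below 60, more than 12 months of amenorrhea, and FSH and estradiol in range. Under note 13, goserelin is ruled out when FSH, LH and estradiol are all in range. Whether note 13 means any or all values out of range makes no difference here, because in the cases below all three are in range.

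**Women with ovaries and all three hormones in range:**

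| Woman | (a) | (b) | (c) | 3.2.5 | Note 13 | Result |
|---|---|---|---|---|---|---|
| Under 60, amenorrhea 12 months or less | no | no | no | required | not given | conflict |
| Under 60, amenorrhea over 12 months | no | no | yes | not required | not given | agree |
| Exactly 60, any amenorrhea duration | no | no | no | required | not given | conflict |
| Over 60 | yes | no | no | not required | not given | agree |

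The third row arises because (a) starts above 60 and (c) stops below 60, so the default clause applies at 60.

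**Grid.** Take ages 48, 59, 60 and 61; oophorectomy yes or no; amenorrhea 5 or 24 months; hormones in or out of range. That is 4 x 2 x 2 x 2 = 32 profiles. Conflicts, all with ovaries and hormones in range:
- ages 48 and 59 at 5 months: 2
- age 60 at 5 and 24 months: 2

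The total is 4 of 32. These are rule combinations, not shares of patients.

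**Consequence per affected woman.** Table 7-1 marks goserelin on day 1 of cycles 1 to 6, which is 6 doses. It marks estradiol on day 1 of cycles 2, 4 and 6, which is 3 tests (weeks 4, 12 and 20 in 5.4.2). Under 3.2.5 she gets 6 and 3; under note 13 she gets 0 and 0. Planned treatment is 6 cycles x 4 weeks = 24 weeks (section 4.3).

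**Opposite direction.** Suppose staff also read note 13 as an instruction to give goserelin whenever hormones are out of range. It would then reach women whom 3.2.5 already counts as postmenopausal:
- age 61, hormones out of range: 2 oophorectomy levels x 2 amenorrhea levels = 4
- ages 48, 59 and 60 with oophorectomy, hormones out of range: 3 x 2 = 6

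That adds 10, giving 4 + 10 = 14 of 32. Note 13 states a necessary condition, so the strict count stays at 4.

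**After rewording.** If note 13 refers to 3.2.5, the two rules are the same and no conflict remains in either direction.

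**The case against.** The strongest reply is that the text favoring 3.2.5 far outweighs a calendar note. The rule that premenopausal women receive goserelin appears in the synopsis and in sections 4, 4.1, 4.3 and 7.1, the last introducing the calendar. Eligibility is reviewed by the investigator or a designee (3.2) and verified by an office (5.1), at a single institution (section 4). The synopsis makes goserelin suppression a condition of eligibility for premenopausal women. All of this stands, and it makes the error less likely. It does not remove it. The general rule does not define premenopausal, and no text gives an order of precedence. The checks are made at enrollment, and this woman can be enrolled under either rule; the slip would come when goserelin is dosed from the calendar.

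A second reply is that the harm is inferred. That is partly right. A reader might infer that these women will regain ovarian function on letrozole. The documents do not say so; they state only the general contraindication before menopause. The 5.6 criterion is not confined to goserelin recipients either, so an unscheduled estradiol test remains possible.

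A third is that the screening line in 5.4.1 is not a second hormone-only rule. It is an item in a list of procedures that also collects medical history. That is accepted, and nothing here rests on it.

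**Conclusion.** The conflict is real on the plain text. It covers women with ovaries and all three hormones in range who are under 60 with 12 months or less of amenorrhea, or exactly 60. Harm arises only if staff dose from note 13; if they follow 3.2.5, there is none. The size per woman is 6 goserelin doses and 3 on-treatment estradiol tests against none. The number of such women cannot be estimated from the documents; with 26 to 38 patients planned (section 4.3) it is probably very small.

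Three stronger readings are not supported. A reader might infer that estradiol is never measured in these women, but it is measured at screening. A reader might infer a fixed 24 weeks of unsuppressed letrozole. In fact 24 weeks is the planned length, and section 4.7 diverts patients with stable disease after 4 cycles, or progression at any time, to surgery or chemotherapy. A reader might also infer an effect on the trial's statistics, but no sample size, stopping rule or error rate depends on this.

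The conclusion assumes that 3.2.5 states the intended definition, and that its default clause applies at age 60 as written. The note should be corrected because it is an operative dosing instruction; the defect does not threaten the trial's conclusions.

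**What to change.** Reword note 13 to: *Administered to all women not postmenopausal per section 3.2.5.* The estradiol tests at weeks 4, 12 and 20 then follow from 5.4.2 and note 15, which need no edit. Adding *per section 3.2.5* to the menopausal-status line in 5.4.1 is optional.

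The cost is up to 6 goserelin doses and 3 estradiol assays for each affected woman, all already required by 3.2.5 and 5.4.2. There is one further effect. If staff had been giving goserelin on hormone values alone, women postmenopausal by age or oophorectomy would no longer receive it or the linked estradiol tests. That agrees with 3.2.5 but should be stated when the change is made.

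Moving criterion (a) to include age 60 is not part of this fix. It would remove goserelin that the protocol now requires for 60-year-olds with ovaries, so it changes who is treated and is for the sponsor to decide separately.
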